4.11.3.4 E-RS diary

E-RS breathlessness (items 7, 8, 9, 10, and 11) and cough items (item 2) will be flagged in the EXACT 14-item e-Diary Tool data listing.

Scores obtained at the E-RS breathlessness scales will be summarized by actual treatment received and visit in terms of absolute values and changes from study baseline as defined in SAP section 4.2.3; a ttest will be used to assess statistically significant difference in the changes from study baseline by actual treatment.

A plot showing the absolute mean change from study baseline by actual treatment received will be provided.

4.11.3.5 This secondary analysis will be executed also on the Completers as a sensitivity analysis. Cough Severity Numerical Rating Scale

A by subject listing will be provided for Cough Severity Numerical Rating Scale as defined in SAP section 4.2.4.

Cough Severity Numerical Rating Scale results will be summarized by actual treatment received and visit in terms of absolute values and changes from study baseline as defined in SAP section 4.2.3.

A plot showing the absolute mean change from study baseline by actual treatment received will be provided.

This secondary analysis will be executed also on the Completers as a sensitivity analysis.

4.11.3.6 PROMIS Item Bank v1.0 Fatigue Short Form 7a Scale

A by subject listing will be provided for PROMIS Item Bank v1.0 Fatigue Short Form 7a Scale as defined in SAP section 4.2.4.

Cough Severity Numerical Rating Scale results will be summarized by actual treatment received in terms of absolute values and change from study baseline at Day 21 as defined in SAP section 4.2.5.

A plot showing the absolute mean change from study baseline by actual treatment received will be provided.

This secondary analysis will be executed also on the Completers as a sensitivity analysis.

4.11.3.7 CGI-C

A by subject listing will be provided for CGI-C as defined in SAP section 4.2.4.

CGI-C results will be summarized based on FAS by actual treatment received in terms of absolute values and change from study baseline at Day 21 as defined in SAP section 4.2.5.

A boxplot showing the mean CGI-C by actual treatment received will be provided.

| Trevi Therapeutics, Inc. | |
|--------------------------|---------------------------|
| TR12 | Statistical Analysis Plan |
| | |

This secondary analysis will be executed also on the Completers as a sensitivity analysis.

4.11.4 Pharmacokinetics

4.11.4.1 Pharmacokinetic Concentrations

Pharmacokinetic plasma concentration of nalbuphine (parent and metabolites), will be listed in Separately set according to SAP section 4.2.4. Listings will include actual sampling times relative to dose administration. Plasma concentrations below the lower limit of quantification (LLOQ) will be presented as Below Limit of Quantification (BLQ) in the listings.

Plasma concentrations of nalbuphine (parent and metabolites) will be summarized by nominal timepoint and as defined in SAP section 4.2.5. The following descriptive statistics will be presented for plasma concentrations obtained at each nominal time point: n, arithmetic mean, SD, coefficient of variation (CV%), geometric mean, geometric CV% (calculated as: $gCV\%=SQRT(e^{s^2}-1)*100$; where s is the standard deviation of the log-transformed values), median, minimum and maximum values.

The following rules will be followed with regards to the number of decimal places and presentation of data in the tables and listings of concentration data:

- Source data shall be used in all derived PK concentrations without prior rounding
- The mean, standard deviation (SD), geometric mean and median will be tabulated to one more significant digit compared to the source data, but with a maximum of four significant digits.
- Minimum and maximum values will be tabulated to the same precision as the source data, but with a maximum of four significant digits.
- Geometric coefficient of variation (CV) % and coefficient of variation (CV%) will be presented to one decimal place.
- 4.11.4.2 Handling of Values Below the Limit of Quantification (BLQ)

All concentrations BLQ or missing data will be labeled as such in the concentration data listings.

Missing samples will be reported as no sample ("NS") and excluded from analysis.

In summary tables, all BLQ values will be set to the ¹/₂*lower limit of quantification (LLOQ), and all descriptive statistics will be calculated.

The number of BLQ values will be reported for each time point

4.11.4.3 Pharmacokinetic Parameters

Not Applicable

4.11.4.4 Pharmacokinetic Analysis

Nalbuphine (parent and metabolites) plasma concentration data will be listed by collection time and nalbuphine dose where applicable. Further PK analyses may be conducted if data allow.

4.11.5 Additional Exploratory Efficacy Evaluation

Responder analysis assessing 30%, 50% and 75% reduction in daytime cough counts

Exploratory variable described in this SAP section 3.2.4

4.12 Number and percentages of subjects with 30%, 50% and 75% reduction from baseline in daytime cough counts will be listed and presented by treatment group. Safety Evaluation

All safety summaries and analyses will be based upon the Safety Set as defined in Section 4.5.

4.12.1 Adverse Events

4.12.1.1 Definition of Adverse Event (AE)

An AE is defined as any untoward medical occurrence in a clinical investigation subject reported on or after the first screening date, which does not necessarily have a causal relationship with this treatment. Adverse events may include the onset of new illness and the exacerbation of pre-existing conditions.

4.12.1.2 Definition of Treatment Emergent Adverse Event (TEAE)

A TEAE is an AE occurring on or after the initial administration of investigational product. In this study, AEs may be treatment emergent with respect to treatment assumed in treatment period 1 or treatment period 2. The following will apply:

- AEs with onset date prior to the date of first of IMP intake in Treatment Period 1 will be considered as AEs non treatment emergent.
- AEs with onset date on or after the date of first IMP intake in Treatment Period 1 (but before first IMP intake in Treatment Period 2) will be considered as Treatment Period 1 TEAE.
- AEs with onset date on or after the date of first IMP intake in Treatment Period 2 will be considered as Treatment Period 2 TEAE.

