BMI = body mass index; PK = pharmacokinetic; AE = adverse event; conmeds = concomitant medications

- = Investigational product administration in each treatment period will be separated by a washout interval of 2 weeks between dosing.
- 2 = Follow-up will occur 14±2 days after the last administration of investigational product.
- 3 = First dose of investigational product for Treatment Period 1 is taken the evening of Day 1 after removal of the cough monitor.
- 4 = Last dose of investigational product for Treatment Period 1 is the morning dose of Day 22.
- 5 = Electrocardiogram (ECG) to be recorded prior to blood sampling when possible at scheduled visits where PK and/or clinical labs are obtained. Subjects should be in the supine position for at least 5 minutes prior to obtaining ECGs with all 3 tracings captured within a 3-5 minute window.
- 6 = Includes heart rate, blood pressure, respiratory rate, body temperature, and pulse oximetry. Vital signs should be taken prior to blood sampling and measured after the subject has been seated for at least 5 minutes.
- 7 = Performance of spirometry should adhere to ATS/ERS guidelines; required as part of meeting inclusion criterion #2.
- 8 = A negative urine pregnancy test will be confirmed prior to randomizing any female subjects of childbearing potential.
- 9 = Blood and urine samples for clinical laboratory testing should be obtained after 8 hours of fasting whenever possible. Clinical chemistry, hematology, urinalysis, and coagulation will be assessed.
- 10 = Baseline values for the purposes of the statistical analysis of treatment effect on daytime cough frequency during that crossover period. First dose of investigational product on Treatment Day 1 will be taken after removal of the cough monitor.
- 11 = Monitor will be placed on the subject by site staff at the end of the visit.
- 12 = Digital cough monitor hookup (24-hour recording); monitor will be worn until the evening of the following day in order to obtain at least a full 24-hour recording period of cough frequency. At the end of each recording session, the monitor will be removed at home by the subject prior to bedtime. On Treatment Day 1, the monitor will be removed prior to taking the first dose of investigational product. Subject to be provided with appropriate shipping material to return monitor for downloading of cough data (after removal).
- 13 = Administered on paper for screening; required as part of meeting inclusion criterion #6.

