- Retrieve, review and re-dispense Subject Medication and Symptom Log
- Collect the investigational product blister card, assess accountability/compliance and return investigational product blister card to subject
- Reminder to take the final dose of investigational product on the morning of the next day (Day 22)
- Instructions for completing the Subjective Opiate Withdrawal Scale (SOWS) daily by e-diary for 14 days (beginning Day 23).
- Record and assess adverse events, concomitant medications, and therapies (including restricted and prohibited medications)

Follow-up Visit 6 (Day 36)

Subjects will return for Follow-up Visit 6 (Day 36) 14 days (+/- 2 days) after the last day of dosing in Treatment Period 1. Subjects will undergo the following assessments:

- Brief physical examination
- ECG (triplicate)
- Measurement of vital signs (blood pressure, heart rate, and respiratory rate), body temperature, and pulse oximetry
- Urine pregnancy test (females of childbearing potential)
- Collect the investigational product blister card and assess accountability/compliance
- Retrieve e-diary
- Retrieve and review Subject Medication and Symptom Log

• Record and assess adverse events, concomitant medications, and therapies (including restricted and prohibited medications)

Before proceeding to Treatment Period 2, females of childbearing potential should have a confirmed negative urine pregnancy test administered by study staff. In most instances, the Baseline visit for Treatment Period 2 will occur on the same calendar day as the Follow-up Visit 6.

6.3.2 Treatment Period 2

Baseline Visit 6 (Day -1)

The Baseline visit for Treatment Period 2 will be completed prior to Day 1 dose administration. Subjects will undergo the following assessments:

- Clinical laboratory testing (chemistry, hematology, urinalysis, and coagulation)
- Serum pregnancy test (females of childbearing potential)
- Contraceptive counseling (if applicable)
- Cough Severity Numerical Rating Scale
- Fatigue Scale (Short Form 7a)
- Re-distribute e-diary to subject, review entries for compliance, and re-train on use
- EXACT version 1.1 e-diary tool and reminder to complete it daily until the next visit
- Dispense cough monitor, re-train subject on use and provide instruction for removing the device prior to bedtime and prior to taking the first dose of investigational product the next day (Day 1)

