6.4 Rationale for Study Design and Dose Selection

This study has been designed as a Phase 2, double-blind, randomized, placebo-controlled, 2 treatment, 2-period crossover study of NAL ER tablets for the treatment of cough in subjects with IPF. Subjects will receive investigational product for 22 days duration during each period of the crossover. The 2 crossover treatment periods will be separated by a 2-week washout period. The published medical literature including the work of *Bacci et al (2018)* concluded that reduction

in daytime cough frequency may be the most relevant clinical endpoint for assessing the efficacy of drug effect in IPF-related cough. Daytime cough is defined as cough that occurs between the time that the subject wakes up and the time that the subject goes to bed.

The primary study endpoint, mean change in daytime cough frequency (coughs per hour), will be analyzed by use of an objective digital recording device, as consistent with the recommendations of *Boulet et al (2015)* who summarized the CHEST Expert Panel recommendations regarding tools to be used in clinical trials assessing cough. The Panel recommended that acoustic cough counting to assess cough frequency should be done through objective means. Secondarily, as supported by the development work of *Bacci et al (2018)*, the E-RS daily diary will be used as a validated patient-reported outcomes (PRO) instrument in assessing NAL ER tablets efficacy in reducing IPF-related cough.

The patients participating in the *FDA's "The Voice of the Patient" (2015)* reported that in addition to cough, the symptoms of shortness of breath and fatigue had the greatest impact on their daily life. Based on this information, and mechanism of action of NAL ER tablets, these additional symptoms may be amenable to treatment and will be investigated with secondary endpoint metrics.

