6.6 Risk/Benefit and Ethical Assessment

Nalbuphine has a long history of use in a parenteral formulation, generally for short-term, episodic use related to surgical interventions. The highest dose proposed in the current clinical study is 162 mg BID (324 mg daily dose), well below the highest recommended daily treatment of 144 mg IV dose (equivalent to 864 mg oral dose) for the currently available parenteral administered product. The high peak plasma concentrations that occur in the setting of parenteral use significantly exceed the peak levels observed with NAL ER oral dosing, an observation that is reassuring with respect to the potential for severe, acute toxicity.

Opiate drug class-related concerns such as the potential for physical dependence, linked to longterm use of opiates, is acknowledged. A requirement for completion of a 2-week safety observation period with daily SOWS reporting has been incorporated into the TR12 study. This will facilitate rapid identification and intervention for the respective relevant risks to subjects.

In addition, labeling of opiate-class drugs includes a warning that concomitant use of an opiate together with a benzodiazepine-class drug can increase the risk for respiratory depression, including a risk for respiratory arrest. This warning is based on post-marketing real world data, assessing the experience with a wide range of drugs in these 2 classes and in varied settings including recreational as well as therapeutic usage. In TR12, concomitant benzodiazepine use is not prohibited, and all subjects are informed of this risk through the study Informed Consent Form. At the time of that consent discussion, subjects who are identified as taking a concomitant benzodiazepine should receive the Patient Information Sheet on this topic, as should any subject for whom a concomitant benzodiazepine is subsequently prescribed.

With respect to the published literature addressing respiratory depression with nalbuphine, one relevant study has been identified; which evaluated the respiratory effects of serial intravenous administration of nalbuphine in healthy volunteers. The results were interpreted by the authors as demonstrating a "ceiling" effect for respiratory depression (*Gal et al 1982*). In previous clinical trials with NAL ER, a total of 41 subjects have received concomitant benzodiazepines while receiving NAL ER, and none of these individuals experienced any event of respiratory depression.

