10.2.3 Adverse Event of Special Interest

As part of a formal investigation of a drug that is classified as CNS active drug within the opioid drug class, certain adverse events will be documented in more detail as part of the analysis to determine any abuse potential of nalbuphine. If a subject spontaneously reports an event, a symptom or a subjective experience that fits any of the 4 categories of AEs described below, that event should be probed with open-ended questions, such as "Can you tell me more about that?" or "Have you ever experienced that kind of feeling before?". The goal is to better understand the context and the potential clinical significance of the event or subjective experience. Importantly, this probing and additional dialogue should take place **ONLY if the subject spontaneously reports such an event or experience**. Pro-active or suggestive questioning is not recommended, since the objective is to understand what the subjects themselves identify as new and different.

Specifically, terms that relate to the following types of events should trigger the collection of additional information under the AESI section of the Adverse Event eCRF:

Categories of Special Interest:

- Experiences or events suggestive of euphoria, such as elation, exhilaration, feeling a sense of exaggerated well-being, or feeling intoxicated.
- Experiences or events suggestive of mood changes or effects, such as reports of sedation, stimulation, or impaired attention/cognition. For example, descriptions of: somnolence,

sedation, lethargy; or agitation, anxiety, restlessness; or abnormal behaviors, labile affect, and depressed mood; or poor attention, and mental or memory impairment.

- Events or descriptions that suggest dissociative or psychotic experiences, such as reports of disorientation, abnormal thoughts, hallucinations, illusions or delusions.
- Observations that suggest events of drug abuse, misuse, dependence or withdrawal. These experiences or observations may be reported by the subject spontaneously (such as reports of feeling addicted, craving investigational product, or complaints of withdrawal after stopping the investigational product). The AE may also be based on direct observations made by the Clinician and/or study staff that suggest inappropriate use of the drug, drug tampering or drug diversion. For example, repetitive or significant single-time events of missing tablets in drug accountability assessments.

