3.2.3 Safety Variables

3.2.3.1 Adverse Events

AEs will be recorded starting with the signing of the informed consent. All AEs will be collected through the follow-up visit of Treatment Period 2.

AEs definitions and analysis are reported in section 4.11.1 of this SAP.

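### The TEAE and AESI summaries pool about 22 dosing days with about 14 washout days, so on-drug and post-treatment incidence are not tabulated separately

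*SAP*

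**What the plan says.** **Dosing and washout.** Protocol 6.4 states: "Subjects will receive investigational product for 22 days duration during each period of the crossover". A note to the schedule in Protocol 6.2 adds: "Last dose of investigational product for Treatment Period 1 is the morning dose of Day 22". Protocol 6.3.1 places the follow-up: "Subjects will return for Follow-up Visit 6 (Day 36) 14 days (+/- 2 days) after the last day of dosing in Treatment Period 1". Period 2 has the same layout.

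**TEAE windows.** SAP 4.12.1.2 credits to Period 1 any event with onset "on or after the date of first IMP intake in Treatment Period 1 (but before first IMP intake in Treatment Period 2". For the second period it says: "AEs with onset date on or after the date of first IMP intake in Treatment Period 2 will be considered as Treatment Period 2 TEAE". SAP 3.2.3.1 sets the end of collection: "All AEs will be collected through the follow-up visit of Treatment Period 2". Both washouts therefore count toward the treatment just stopped.

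**Tables.** The TEAE tables in SAP 4.12.1.8 use the grouping of SAP 4.2.5, which is treatment received. They cut by SOC and PT, relatedness, grade, seriousness and action taken, but not by dosing versus washout. AESIs are tabulated only as rows of the overall summary (any, related, serious, related serious), without category or preferred term.

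**Role of the washout.** Protocol 6.6, on physical dependence, says: "A requirement for completion of a 2-week safety observation period with daily SOWS reporting has been incorporated into the TR12 study". Protocol 10.2.3 makes withdrawal an AESI category, with spontaneous reports such as "feeling addicted, craving investigational product, or complaints of withdrawal after stopping the investigational product". The same AESI set includes somnolence and sedation, which Protocol 6.5 lists among the effects expected on drug.

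**The concern.** The protocol asks two safety questions: how well NAL ER is tolerated during titration and dosing, and what happens when it is stopped. One TEAE interval per treatment answers neither on its own. Background events in the washout enter both columns and can blunt the on-drug contrast. Any events caused by stopping enter the NAL ER column only and look like intolerance. The AESI rows show this best, because sedation during titration and a withdrawal complaint after the last dose add up to one count.

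Safety and tolerability is a primary objective (SAP 2.1). The protocol synopsis plans no formal analysis of safety outcomes and leaves any inference to clinical review, so these descriptive tables carry much of the safety result.

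**Working it through.** **1. Window length (the plan's own figure).** Inputs: 22 dosing days (Protocol 6.4) and follow-up 14 ± 2 days after the last dosing day (Protocol 6.3.1). 22 + 14 = 36, which reproduces the stated Day 36; the range is Day 34 to Day 38.

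**2. Off-drug share.** 14/36 = 39%. With the visit window it runs from 12/34 = 35% to 16/38 = 42%. Early stoppers have a larger share. For a stop on Day 9 it is 14/(9 + 14) = 61%. If the discontinuation visit comes the full two weeks later and follow-up two weeks after that, as Protocol 6.3.3 allows, it is 28/(9 + 28) = 76%.

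**3. Any-TEAE row, background only.** The documents give no event rates, so these are assumptions: constant background hazard, placebo incidence p0 = 30% over 22 days, NAL ER multiplying the hazard by 2.5 while dosing, and no effect after stopping.

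- On-drug incidence: 1 − 0.70^2.5 = 59.0%, against 30.0%. Ratio 1.97, difference 29.0 points.
- Background risk in the washout: q = 1 − 0.70^(14/22) = 20.3%.
- Pooled NAL ER: 1 − (1 − 0.590)(1 − 0.203) = 67.3%.
- Pooled placebo: 1 − (1 − 0.300)(1 − 0.203) = 44.2%.
- Pooled contrast: ratio 67.3/44.2 = 1.52, difference 23.1 points. The difference shrinks by the factor 1 − q = 0.797.

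For placebo incidence of 20% to 40% and a hazard ratio of 2 to 3, an on-drug ratio of 1.6 to 2.4 becomes 1.3 to 1.8.

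**4. A single preferred term with low background.** Assume 40% vs 5% on drug. Then q = 1 − 0.95^(14/22) = 3.2%, and the pooled figures are 41.9% vs 8.1%. The difference goes from 35.0 to 33.9 points. The ratio falls from 8.0 to 5.2, but the clinical message does not change.

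**5. Adding withdrawal events.** Suppose NAL ER also causes a washout event in a fraction w of the subjects who would otherwise be event-free. In step 3, the pooled difference becomes 0.231 + 0.327w, where 0.327 = 0.410 × 0.797. It equals the on-drug 0.290 at w = (0.290 − 0.231)/0.327 = 0.18. Below that value pooling understates the on-drug difference, and above it pooling overstates it. For the term in step 4 the break-even is (0.350 − 0.339)/0.581, about 0.02, where 0.581 = 0.60 × 0.968. The direction therefore depends on a quantity that the planned AE tables do not show.

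**The case against.** The strongest objection is that the washout is already covered. SOWS is completed daily for 14 days after the last dose (SAP 3.2.3.10) and summarised by treatment and study day (SAP 4.12.10). AE listings give onset date and relative study day (SAP 4.2.4, 4.12.1.8), and AESI listings also give the time from the last dose. Protocol 11.8.1 adds narratives for abuse-related AESIs. A reader might infer from the pooled tables that withdrawal-phase events cannot be seen. The documents do not support that: an anxiety event on Day 24, if reported, can be placed after the last dose from the listings.

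What these sources lack is AE incidence by treatment and phase. Listings give no incidence. SOWS is a symptom scale, not AE incidence with grade and seriousness. Study day also counts from first intake (SAP 4.2.2), so a SOWS summary by study day does not align early stoppers on time since last dose.

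A second objection is that other tables protect the on-drug question. Tables of events leading to interruption or withdrawal of IMP are essentially confined to dosing, and the related-event tables remove some background. Both points stand. However, an event caused by stopping may itself be judged related, so the related tables still mix the phases.

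Third, the SAP window agrees with the protocol, which also sets no end-of-exposure limit (Protocol 10.1, 11.8.1). That is correct: running the TEAE window past the last dose is not an error. On-drug events are not lost, and both treatments get the same added interval.

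**Conclusion.** The point holds as a gap in tabulation. Every TEAE and AESI summary uses a window that is about 39% off drug for a subject who completes dosing, and none separates incidence on drug from incidence after stopping.

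The size depends on rates that the documents do not give. For a broad row with 30% background and a 2.5-fold on-drug hazard, the loss is about 6 points of difference (29 to 23) and a ratio of 1.97 falling to 1.52. For a low-background term it is about 1 point.

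A reader might also infer that pooling always pulls the contrast toward no difference. That follows only if NAL ER causes no events on withdrawal. If it does, the net bias can go either way, and the pooled tables cannot show which case applies. This is a worthwhile, inexpensive improvement and not a flaw in the TEAE definition.

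**What to change.** Keep the TEAE definition in SAP 4.12.1.2 and the planned tables, and add to 4.12.1.8:

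- A phase flag for each TEAE, set by onset date against the last IMP date of the period. On-treatment runs from first to last dose. Post-treatment runs from then to the next period's first dose or the end of follow-up. Count an event by its onset, even if it continues into the washout.
- An explicit statement of any residual-effect lag after the last dose. The documents give no figure, so any lag must be labelled an assumption.
- A rule for partial onset dates, extending SAP 4.12.1.7.
- The overall, SOC/PT and AESI tables by treatment received within each phase. Rates per subject-day would allow for unequal window lengths in early stoppers.

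No new data are needed: onset dates are collected, and the last IMP intake already bounds exposure in SAP 4.10.1. The cost is one derived variable and a set of repeat tables. Some of these will have small counts, particularly as recruitment stopped before the planned sample size (SAP 4.14, 4.15), so they should be read as descriptive.
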